B: One single positive culture obtained from aspiration of synovial fluid regardless of microorganism AND any antibiotic prescriptions (ATC category J01) redeemed

These definitions of PJI-likely are based on a modified version of EBJIS (33) as described previously (see primary outcome) and the study by Milandt *et al.* (40) where first-time revisions with one positive culture were found to have a higher risk of re-revision for PJI.

Cases of PJI-likely, will be captured in HAIBA and MIBA, and registration of antibiotic prescription in NPR. Positive culture samples (aspirations, tissue biopsies or fluid) must be obtained from the relevant hip joint.

3) Length of stay for hospitalization (LOS)

Length of hospital stay (continuous measure [days]) is defined as number of postoperative overnight stays, including transfers to other departments and hospitals within 24 hours. Data on LOS is acquired from DNPR.

4) Major Adverse Cardiovascular Events

Incidence of Major Adverse Cardiovascular Events (MACE). A MACE is defined a priori to include thromboembolic complications including venous thromboembolism, myocardial infarction, atrial fibrillation and stroke based on the diagnostic ICD10 codes listed in Appendix B. VTE is defined a priori as both deep venous thromboembolisms confirmed by compression ultrasound and pulmonary embolism confirmed by spiral computed tomography (CT), ventilation-perfusion scintigraphy or pathological removal of an embolus and based on the following diagnostic ICD10 codes: I26, I80.1-I80.9, I82.1-I82.9, or T81.7B-D. Data will be extracted from DNPR.

5) Hospital-treated infections (Other than those listed above)

Patients with at least one hospital-treated infection are defined as those with first-time hospital admission for a primary or secondary infection diagnosis following discharge from the index THA surgery. Hospital-treated infections are identified from DNPR based on ICD-10 codes listed in Appendix B. The list of infections includes chronic and more rare infections, to detect possible flare-ups in any possible ongoing infections. This outcome does not include infections treated during index admission for arthroplasty surgery.

6) Community-based antibiotic use

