Community-based antibiotic use (any community-treated infection or antibiotic use after discharge) is defined as at least one dispensing after discharge from index THA surgery and broad-spectrum antibiotics based on the Anatomical Therapeutic Chemical classification (ATC) codes. All antibiotics in Denmark require prescriptions from a physician. The Danish National Health Service Prescription Database has registered all reimbursed prescriptions from all community pharmacies since 2004. Medications are coded according to the ATC codes listed in Appendix B. All antibiotics in Denmark require prescriptions from a physician and these will be identified using NPR (41). We aim to specifically examine the redemption of ATC code J01E prescriptions within one week following the index operation to capture instances of post-operative urinary tract infections.

7) Opioid use

Patients who received at least one opioid prescription following primary THA surgery. All opioids in Denmark require prescriptions from a physician and these will be identified using NPR (41). The following ATC codes (including all subcodes) are included: N01AH (opioid anesthetics), N02A (opioids), N07BC02 (methadone), and R05DA04 (codeine). Given the lack of a clear definition for opioid users, we defined opioid users as patients who redeemed two opioid prescriptions within six months prior to THA surgery. Conversely, patients who did not redeem two or more opioid prescriptions within this timeframe were classified as opioid naïve. For opioid naïve patients, opioid use post-THA is defined as the redemption of two opioid prescriptions within 90 days following surgery. We assert that two separate redeemed prescriptions confirm actual medication use. We will calculate the treatment dosage based on the number of packages and volume redeemed within 90 days post-surgery. To investigate dosages, all doses will be converted to morphine milligram equivalents using a conversion factor specific to the type of opioid (42, 43).

8) Use of acetaminophen or non-steroidal anti-inflammatory drugs

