	
H60.0, J34.0A, J36, J38.3D, J38.7G, J39.0, J39.1, J39.8A, J85.1, J85.2, J85.3, K04.6, K04.7, K11.3, K12.2, K13.0A, K14.0A, K20.9A, K35.3A, K35.3B, K57.0, K57.2, K57.4, K57.8, K61, K63.0, K65.0, K75.0, K81.0A, K85.8A, L02, L05.0, L05.9, M60.8A, M86.8A, M86.9A, N15.1, N34.0, N41.2, N45.0, N48.2, N49.2A, N61.9A, N61.9B, N70.0A, N70.0B, N71.0A, N73.0A, N73.0B, N73.2A, N73.2B, N73.3A, N73.5A, N73.8A, N73.8C, N75.1, N76.4, N76.8A, Except: A54.1B, B43.0, B43.8, B43.9, K57.0B, K57.0C, K57.2B, K57.2C, K57.4A, K65.0M, K65.0N, K65.0O, K65.0P, A46, H01.0, H03, H60.0, H60.1, H60.2, H60.3, H62, K12.2, K13.0, K61, M72.6, L01, L08, L03, J34.0, L00, L02, L04, L05, L06, L07, L30.3, L73.8, H00, H01.0, H03.0, H03.1, H04.3, H05.0, H06.1, H10, H13.0, H13.1, H15.0, H19.1, H19.2, H22.0, H32.0, H44.0, H44.1, H60, H61.0, H62.0, H62.1, H62.2, H62.3, H65, H66, H67.0, H67.1, H68, H70, H73.0, H75.0, H83.0, H94.0 Except: H60.4, H60.4A, H605, H60.5B, H60.8, H608.A, H65.2, H65.3, H65.4, H65.4C, H66.1, H66.2, H66.3, H68.1, H70.1, H70.8, G00 -07, A80 - A89, G00, G01, G02, G03, A32.1, A39.0, A17.0, A20.3, A87, A54.8D, A02.2C, B37.5, B00.3, B01.0, B02.1, B05.1, B26.1, B38.4, A00 -A09, K35, K37, K57.0, K57.2, K57.4, K57.8, K61, K63.0, K65.0, K65.9, K67, K75.0, K75.1, K80.0, K80.3, K80.4, K81.0, K81.9, K83.0, K85.9, I00 -I02,

--	--

		
I30.1, I32.0, I33, I38, I40.0, I39.8, B37.6, J00 - J06, J36, J39.0, J39.1, J12 -J18, J20 - J22, J44.0, J85.1, J86, J20 -J22, J34.0, J35.0, J38.3C, J38.3D, J38.7B, J38.7F, J38.7G, Except: J34.0E, J34.0F, J34.0G, J34.0H, N10, N11, N12, N15.1, N15.9, N30, N33.0, N34, N39.0, N08.0, N13.6, N16.0, N28.8D, N28.8E, N28.8F, N29.0, N29.1, Except: N30.1, N30.2, N30.4, A50 -A64, N41, N45, N48.1, N48.2, N49, N51.1, N51.2, N70 -77, O23, O26.4, O41.1, O74.0, O75.3, O85, O86, 088.3, O91, O98, M00, M01, M86, M63.0, M63.2, T80.2, T81.4, T82.6, T82.7, T83.5, T83.6, T84.5, T84.6, T84.7, T85.7, T88.0, T89.9, B90 -B99, K04.0, K05.2
 
Codes for specific Hospital-treated infections
 
Pneumonia: J12-J18
 
Urinary tract infections N10, N11, N12, N15.1, N15.9, N30, N33.0, N34, N39.0, N08.0, N13.6, N16.0, N28.8D, N28.8E, N28.8F, N29.0, N29.1, Except: N30.1, N30.2, N30.4

Community-based antibiotic use	The Danish National Prescription Registry (NPR)	
Narrow spectrum antibiotics: J01CE, J01CF, J01DB
 
Broad spectrum antibiotics: J01DC, J01DD, J01DE, J01DH, J01DI, J01CR, J01CA, J01F, J01E, J01MA, J01AA

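### Key secondary endpoint 6 is labelled as any antibiotic use after discharge, but its Appendix B list covers only part of ATC J01 and its definition leaves the role of narrow-spectrum drugs open

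*SAP*

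**What the plan says.** The definition is in the SAP under key secondary endpoints, item 6: "Community-based antibiotic use (any community-treated infection or antibiotic use after discharge) is defined as at least one dispensing after discharge from index THA surgery". The same sentence then continues "and broad-spectrum antibiotics based on the Anatomical Therapeutic Chemical classification (ATC) codes". The codes are fixed by reference: "Medications are coded according to the ATC codes listed in Appendix B".

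Appendix B, in the row for this outcome, gives two lists:

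- "Narrow spectrum antibiotics: J01CE, J01CF, J01DB"
- "Broad spectrum antibiotics: J01DC, J01DD, J01DE, J01DH, J01DI, J01CR, J01CA, J01F, J01E, J01MA, J01AA"

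There is no third class and no row for J01 as a whole. Table 2 has one row for the outcome.

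Item 2 of the same section (PJI-likely, criterion B) uses the same prescription registry but counts "any antibiotic prescriptions (ATC category J01) redeemed". The Appendix B row for PJI-likely likewise names the whole J01 category.

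Item 6 closes with a further intention, aimed at urinary infections: "We aim to specifically examine the redemption of ATC code J01E prescriptions within one week following the index operation to capture instances of post-operative urinary".

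**The concern.** The label promises every antibiotic redeemed after discharge, while the code list delivers a subset. A redemption outside the 14 listed subgroups counts as an antibiotic for PJI-likely and as no antibiotic for endpoint 6, and the SAP gives no reason for the difference.

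The defining sentence adds a second uncertainty. A dispensing joined by 'and' to broad-spectrum antibiotics can mean any listed antibiotic, broad-spectrum only, or two separate outcomes. An analyst could build three different variables, with one Table 2 row to put them in. The SAP makes no multiplicity adjustment for key secondary endpoints, so a choice made after seeing data would go unchecked.

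This endpoint covers infection treated outside hospital, one place where a cost of shorter prophylaxis could appear. Its absolute rates should mean what the label says.

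**Working it through.** **Step 1. Scope of the list.** Appendix B has 3 narrow-spectrum and 11 broad-spectrum codes: 3 + 11 = 14. Matching codes by prefix gives:

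| Code group | On Appendix B list | In J01 (PJI-likely criterion B) | In J01E |
|---|---|---|---|
| J01X | no | yes | no |
| J01G | no | yes | no |
| J01B | no | yes | no |
| J01CA | yes | yes | no |
| J01E | yes | yes | yes |

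A patient whose only redemption falls in one of the first three rows is scored as having no community antibiotic use. J01CA and J01E redemptions after discharge are scored as use.

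**Step 2. Number misclassified.** The SAP states no expected rate for this endpoint, so there is no figure of its own to reproduce. Both inputs here are assumptions: true use *p* of 10–30%, and a share *m* of 2–20% of users who redeem only unlisted codes.

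Users scored as non-users per 10,000 patients = 10,000 × *p* × *m*

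- Low end: 10,000 × 0.10 × 0.02 = 20
- Middle: 10,000 × 0.20 × 0.10 = 200
- High end: 10,000 × 0.30 × 0.20 = 600

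**Step 3. Effect on the comparison.** Take 10,000 patients per group (the SAP's upper anticipated number), an assumed true relative risk of 1.10 for single versus multiple dose, and the same *m* in both groups. Each observed rate is the true rate × (1 − *m*).

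With *p* = 20% and *m* = 10%:

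- True rates 22% and 20%: OR = (0.22/0.78) / (0.20/0.80) = 1.128; risk difference 2.0 points.
- Observed rates 19.8% and 18%: OR = (0.198/0.802) / (0.18/0.82) = 1.125; risk difference 1.8 points.

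Power uses a two-sided 5% normal approximation, ignoring clustering: Φ(|difference| / SE − 1.96), with SE = √[(p₁(1−p₁) + p₂(1−p₂)) / 10,000].

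- True: SE = √[(0.1716 + 0.16) / 10,000] = 0.00576; 0.02 / 0.00576 − 1.96 = 1.51; power 0.935.
- Observed: SE = √[(0.1588 + 0.1476) / 10,000] = 0.00554; 0.018 / 0.00554 − 1.96 = 1.29; power 0.902.

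The same calculation at three points:

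| *p* | *m* | OR true → observed | Risk difference, points | Power |
|---|---|---|---|---|
| 10% | 20% | 1.112 → 1.110 | 1.0 → 0.8 | 0.636 → 0.532 |
| 20% | 10% | 1.128 → 1.125 | 2.0 → 1.8 | 0.935 → 0.902 |
| 30% | 20% | 1.149 → 1.136 | 3.0 → 2.4 | 0.995 → 0.974 |

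The absolute quantities shrink by the factor 1 − *m*; the odds ratio barely changes. The footnote to Table 2 derives the risk difference from the odds ratio and the multiple-dose baseline risk, so an understated baseline carries straight into that column.

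**The case against.** The best defence is that different purposes may use different code sets. In PJI-likely, J01 is only a qualifier joined to a positive synovial culture, so a broad set does little harm there; for a stand-alone endpoint, a selected list could be deliberate, to leave out use unrelated to infection. It is also one of nine key secondary endpoints, which the SAP says will be interpreted with caution. This has some force: the difference from PJI-likely alone would not prove an error. But item 6 contradicts itself, with an 'any' label over a partial list and no stated reason for the selection.

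A reader might infer that the omission biases the comparison between regimens. The documents do not support that. Every centre gives both regimens, and the model has a centre random effect and a period effect, so stable local prescribing habits largely cancel. Nothing in the SAP suggests that unlisted codes would be used more under one regimen.

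A reader might also infer that the week-one J01E rule turns real courses into 'no use', or that it misses most urinary infections. The first does not follow: a J01CA redemption on day 4 or a J01E redemption on day 12, if after discharge, still counts in endpoint 6. The rule is worded as an extra look, has no Table 2 row and decides nothing. The second needs figures on which drugs treat urinary infection in these patients, and when; the SAP has none. What stands is narrower: one code group in one week describes early J01E use and cannot by itself be read as a count of all post-operative urinary infections.

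**Conclusion.** The point holds as a defect of definition. Followed literally, the plan scores patients with only unlisted J01 redemptions as non-users, against its own label, and it does not settle whether narrow-spectrum dispensings count. The consequence is understated absolute rates and an understated risk difference. Under the assumed ranges that is 20 to 600 patients per 10,000; the true number cannot be obtained from the SAP. If under-capture is equal in both groups, the odds ratio is almost unaffected and the loss of power ranges from negligible to about 10 percentage points (0.636 to 0.532, at 10% use with 20% of users missed). The primary endpoint is not touched. The correction is worth making because it is cheap and removes a choice from the analyst.

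**What to change.** In item 6 and in the Appendix B row:

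1. Define community-based antibiotic use as at least one redemption of any J01 code after discharge and within 90 days of surgery, in line with PJI-likely criterion B.
2. Delete the words about broad-spectrum antibiotics from the defining sentence.
3. Report narrow-spectrum, broad-spectrum and other J01 as a descriptive split, keeping the present two lists for the first two classes.
4. Label the week-one J01E look as an exploratory description of early J01E use, not as a measure of all post-operative urinary infections. Its code and window can stay.

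The cost is a few lines of wording and code, on prescription data the trial already plans to use. The small downside is that the wider definition takes in some J01 use unrelated to infection; the other-J01 class makes this visible. The change should be fixed before the randomization code is unsealed.

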than those listed above), Community-based antibiotic use, Opioid use, Use of prescribed acetaminophen or non-steroidal anti-inflammatory drugs, Any revision after THA.

STUDY METHODS

Trial design

The Pro-Hip-Quality OA trial is designed as a pragmatic registry-based, multicenter, open-label, cross-over, cluster-randomized, non-inferiority trial (13-16). The statistical analysis plan (SAP) and trial protocol are reported in accordance with a pragmatic combination of the following CONSORT statements: ‘CONSORT for trials conducted using cohorts and routinely collected data (13)’, ‘Pragmatic Trials (14)’ ‘Cluster Randomized Trials (15),’ ‘Randomized Crossover Trials (16)’ and ‘Noninferiority and Equivalence Randomized trials (17).’ This pragmatic registry-based trial design (18) will include cluster randomization of 36 different clinical departments, applying a crossover design. The trial was designed as a nationwide study where all public and private orthopedic departments participated, and all eligible patients were included.

The cluster randomization with embedded cross-over design across 36 clinical centers ensures that each center will administer a specific antibiotic regimen (i.e., either single-dose or multiple-dose) for one year. After the first year, centers will switch to the alternate regimen. This design ensures that each center experiences both interventions over the two-year study, facilitating a balanced comparison between the two treatment protocols. We do not anticipate significant variations in patient characteristics between those enrolled in year 1 and year 2 of the study. This expectation encompasses consistency in key factors: patient demographics (e.g., age, sex), comorbidities, baseline health conditions, disease severity, and treatment indications. Similarly, we do not foresee substantial changes in the clinical setting or study environment over the two years, including protocols for patient recruitment, infection prevention strategies, surgical methods, diagnostic approaches, revisions surgery, or access to healthcare resources. Furthermore, the crossover approach means that the sites are randomized to receive each of the interventions once during separate periods (i.e., study year 1 and 2) acting as their own control group. This may attenuate possible imbalances and variations in site characteristics (19, 20).

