Choice of the non-inferiority design will enable the deliverance of substantial evidence to change clinical practice if the prevention of PJI with a single dose of prophylactic antibiotic is “no less effective than” antibiotic practices of longer duration (i.e., multiple doses). Members of the Danish orthopedic community have been involved in deciding the potentially increased serious infection rate difference, we are willing to tolerate. Because the sample size is based on the standard flow of THA within the Danish real-world setting, we did not conduct formal power or sample size calculations. Initially, we defined “appreciably worse” serious infection rates and the chances of an erroneously significant result, that is, a false positive, that the medical community will tolerate. The PJI rate in Denmark is between 0.5% and up to 5,1%, (mean 1,2%; 95% CI: 1,0-1,4) varying at departmental level (21). It was decided that we will be willing to tolerate a potentially increased serious infection risk difference of up to 0.1% (1‰ more having a PJI i.e., up to one per thousand).

Confidence intervals and p-values

All 95% confidence intervals (95%CIs) and *P*-values will be two sided. We will not apply explicit adjustments for multiplicity, rather we will interpret the key secondary endpoints with caution.

Primary endpoint: If we assume that the PJI risk is similar in the two groups (with 10,000 patients in each) we expect to achieve a precision (narrowness) in the two-sided 95% confidence intervals around the Odds Ratio (OR=1.000) from a Generalized Linear Mixed Model (GLMM), with 95% limits from 0.756 to 1.323; with a Random Effects factor for the 36 individual centers, and Fixed Effect factors for group, period and the interaction between group and period (Group \times Period). This was validated through multiple simulations. The same simulations were carried out with a population of 8,000 in each group for sensitivity, resulting in 95 % limits around the Odds Ratio (OR=1.000) from 0.731 to 1.368. Based on the CIs from these simulations, that

have very little variability, and the clinical importance of PJIs, a pragmatic non-inferiority margin should be chosen. Thus, non-inferiority will be shown if the upper limit of the two-sided 95% confidence interval for the odds ratio (derived from the GLMM) is less than 1.4 for the single dose as compared with the multiple doses group.

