The primary analyses will be based on the Intention to Treat (ITT) population, i.e., all patients undergoing the prespecified surgery corresponding to the specific year (cross-over, cluster randomization). Two-sided 95% confidence intervals will be estimated and reported enabling (standard) superiority interpretations. The primary statistical analysis model will be based on a *Generalized Linear Mixed Model*, with a random effects factor applied indexing the clinical center (36 levels: 1, 2, 3, ..., up to 36), a fixed effect will be applied for period (2 levels: 1st and 2nd year, respectively), and antibiotics group (2 levels: Single-dose and Multiple-dose, respectively), as well as the interaction between the two period and antibiotics group (period×group; 4 levels: 2×2 levels). For the primary endpoint: Noninferiority will be shown if the upper limit of the two-sided 95% CI for the odds ratio is less than 1.4 for the single antibiotic doses as compared with multiple doses.

In addition, subgroup analyses will be performed to examine the following known and suspected baseline risk factors for PJI infection will be compared: age (≥ 65 versus < 65 years), sex (male versus female), Anthropometric categories (BMI: ≥ 30 versus $< 30 \text{ kg/m}^2$) as well as morbid obesity (BMI: ≥ 40), and presence of diabetes (with versus without). Additional analyses of the study will assess whether the difference of PJI risk in the two treatment arms differ in specific subsets of patients: femoral stem cementation (antibiotic-loaded bone cement versus bone cement with no antibiotic-load and cementless fixation vs fixation with bone cement) and type of antibiotic (beta-lactam antibiotics versus other). The rationale for these analyses is that we suspect the risk of infection to be different in these subgroups. The pharmacokinetics of the antibiotics might have an impact on the infection rates in the relevant groups. The statistical approach for this evaluation of potential effect modifiers is a test for statistical interaction to evaluate whether the treatment effect varies across levels of the effect modifier (46).

Finally, blinded results from the statistical analyses (single-dose compared to multiple-dose) will be presented to the author group followed by development of two written interpretations. The author group will sign a consensus statement comprising both interpretations prior to the unsealing of the randomization code.(47)

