Outcome	Single-dose (N =)	Multiple- dose (N =)	Odds Ratio (95% CI)	†Absolute risk difference (95%CI)
Primary Outcome				
Prosthetic Joint infection at 90 days, no. (%)				
Key Secondary Outcomes				
Serious adverse events (SAE), no. (%)				
PJI-likely, no. (%)				
Major Adverse Cardiovascular Events, no. (%)				
Length of stay (LOS), days				
Hospital-treated infections (excluding SSI), no. (%)				
Community-based antibiotic use, no. (%)				
Opioid use, no. (%)				
Use of acetaminophen/non-steroidal anti-inflammatory drugs , no. (%)				
Revision due to any cause, no. (%)				

* The primary analyses will be based on the Intention to Treat (ITT) population based on the Full Analysis Set; i.e., all patients undergoing the prespecified surgery using the antibiotic dose corresponding to the specific year (cross-over, cluster randomization). Two-sided 95% confidence intervals will be estimated and reported enabling (standard) superiority interpretations. The primary statistical analysis model will be based on a *Generalized Linear Mixed Model*, with a random effects factor applied indexing the clinical center (36 levels: 1, 2, 3, ..., up to 36), a fixed effect will be applied for period (2 levels: 1st and 2nd year, respectively), and antibiotics group (2 levels: Single-dose and Multiple-dose, respectively), as well as the interaction between the two (period×group; 4 levels: 2×2 levels). Hierarchical models account for variations in baseline risk across clusters (e.g., sites or patient subgroups). †Absolute risk differences and their 95% confidence intervals will be derived from odds ratios and corresponding 95% confidence intervals estimated by the hierarchical model, incorporating the baseline risk in the reference group (multiple-dose). The 95% confidence intervals will not be adjusted for multiplicity and should not be used in place of hypothesis testing.

Table 3. Serious Adverse Events within 90 days within each group. *

Events	Single-dose (N =)	Multiple-dose (N =)	Odds ratio (95% CI)	Absolute risk difference [†]
Serious adverse event — no. (%)				
Any infection requiring intravenous antibiotics				
Severe allergic reaction				
Organ failure				
Life-threatening events				
Musculoskeletal				
Deep infection				
Hip dislocation				
Femoral fracture				
Aseptic loosening				
Cardiovascular				
Vascular injury				
Pulmonary embolism				
Deep venous thrombosis				
Acute myocardial infarction				
Stroke				
Nervous system				
Nerve injury				

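### With group×period in the primary model there is more than one group odds ratio, and the SAP does not say which one is tested against 1.4

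*SAP*

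**What the plan says.** - **Design.** Under Trial design, "each center will administer a specific antibiotic regimen (i.e., either single-dose or multiple-dose) for one year" and then switches. Centres are described as "acting as their own control group".
- **Primary model.** Analysis methods specifies a generalized linear mixed model "with a random effects factor applied indexing the clinical center (36 levels: 1, 2, 3, ..., up to 36"), with fixed effects for period and antibiotics group, "as well as the interaction between the two period and antibiotics group". The Table 2 footnote repeats this. The section Confidence intervals and p-values uses the same structure for the expected precision: "Fixed Effect factors for group, period and the interaction between group and period".
- **Decision rule.** "Noninferiority will be shown if the upper limit of the two-sided 95% CI for the odds ratio is less than 1.4". The odds ratio is in the singular, and no contrast is named.
- **Expected precision.** At OR = 1.000 the limits are 0.756 to 1.323 with 10,000 patients per group, and 0.731 to 1.368 with 8,000. The event rate used in the simulations is not given.
- **Software.** R with lme4 and emmeans. No factor coding, contrast or averaging rule is stated.

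**The concern.** A model with group, period and their interaction has no single group effect. It has one per year, plus any average of the two. The rule compares one number with 1.4, so the plan has to say which.

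The choice matters because the candidates differ in kind. A one-year contrast compares centres on single dose with other centres on multiple dose in the same year. It uses about half the patients and carries the between-centre differences in infection risk that the crossover is meant to remove. The averaged contrast uses both years, with each centre as its own control. The same fitted model could therefore meet the margin on one OR and miss it on another. The absolute risk differences in Table 2 are derived from the ORs and inherit the ambiguity.

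**Working it through.** **1. Aliasing.** Let G = 1 for single dose, T = 1 for year 2, and S = 1 for centres that start on multiple dose. The four cells (G,T) = (1,0), (0,1), (0,0), (1,1) have S = 0, 0, 1, 1, so S = 1 − G − T + 2·G·T exactly. The design matrix [1, G, T, G×T] has rank 4, and adding S leaves it at 4. The interaction cannot be separated from sequence or carry-over.

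**2. The candidate ORs.** Write the fixed part as a + bG + cT + dGT. The log OR is b in year 1, b + d in year 2, and b + d/2 averaged. With treatment coding (R's default) and year 1 as reference, the printed group coefficient is b. Substituting GT = (S − 1 + G + T)/2 shows that b + d/2 is the group coefficient in a model with group, period and sequence. This is why averaging keeps the within-centre comparison.

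**3. The SAP's own figure.** Stated limits: SE = ln(1.323/0.756)/3.92 = 0.143. Closed form: SE = √(2/(n·p·(1−p))), with n patients per group and risk p.

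| Contrast | n per group | p (assumed) | 95% limits at OR 1 |
|---|---|---|---|
| Two years | 10,000 | 1.0% | 0.757–1.321 |
| Two years | 8,000 | 1.0% | 0.732–1.365 |
| One year | 5,000 | 2.0% | √(2/98.0) = 0.1429; 0.756–1.323 |
| One year | 4,000 | 2.0% | √(2/78.4) = 0.1597; 0.731–1.368 |

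The two-year contrast reproduces the stated limits closely at about 1% risk. A one-year contrast reproduces them to three decimals at 2% risk. The SAP gives a mean rate of 1.2% (95% CI 1.0 to 1.4), which makes 2% the less natural input, but the simulated rate is not stated.

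**4. One-year contrast, taking 0.143 as the two-year SE.** Half the patients give SE = 0.143 × √2 = 0.202. Between-centre SD τ adds 2τ²/18 to the variance, assuming 18 centres per sequence and equal centre sizes. The chance of meeting the margin at true OR 1 is Φ(ln 1.4/SE − 1.96), with ln 1.4 = 0.3365.

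| Contrast | τ (assumed) | SE | Upper limit at OR 1 | Chance of upper limit < 1.4 |
|---|---|---|---|---|
| Two-year | – | 0.143 | 1.32 | Φ(0.397) = 65% |
| One-year | 0 | 0.202 | 1.49 | Φ(−0.293) = 38% |
| One-year | 0.3 | 0.225 | 1.56 | Φ(−0.467) = 32% |
| One-year | 0.5 | 0.262 | 1.67 | Φ(−0.675) = 25% |

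**5. Simulated mixed-model fits** (36 centres, 18 per sequence, unequal sizes, 10,000 per group, true OR 1, τ = 0, 0.3, 0.5; 150 runs per setting, so about ±8 percentage points).

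| Risk | Analysis | Mean upper limit | Chance of upper limit < 1.4 |
|---|---|---|---|
| 1.0% | No interaction | 1.325–1.330 | 61–73% |
| 1.0% | Interaction, averaged | 1.327–1.333 | 58–73% |
| 1.0% | Interaction, treatment-coded group coefficient | 1.505–1.693 | 27–39% |
| 1.2% | No interaction | 1.292–1.295 | 71–80% |
| 1.2% | Interaction, averaged | 1.294–1.296 | 71–80% |
| 1.2% | Interaction, treatment-coded group coefficient | 1.446–1.640 | 30–44% |

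A further check at 1% risk gave about 24–36% for the group coefficient and about 65% for the averaged contrast, consistent with the above. At 1% risk the coefficient's mean SE rises with τ (0.209, 0.226, 0.269), while that of the averaged contrast stays at 0.144–0.147. The one-year coefficient carries between-centre variance and the averaged contrast essentially does not.

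**The case against.** The best case for the plan is that averaging is already implied. Adherence and protocol deviations defines the estimand as the average effect among all randomized centres, which a one-year contrast fits poorly. Table 2 has one OR per outcome against whole-group numbers. The package list includes emmeans, whose default group contrast averages over period with equal weights. Once averaged, the interaction costs almost nothing: simulated SE 0.133–0.146, against 0.132–0.145 without it. No section interprets the interaction or makes the conclusion depend on it.

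Most of this stands. A reader might infer that the primary OR simply is a one-year, between-centre comparison. The SAP does not support that: it holds only if treatment coding is used and the raw coefficient is taken as the answer, and the SAP states neither. A reader might also infer that the term ruins the primary model, but the averaged contrast shows otherwise.

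What does not stand is that the stated precision settles the matter. A reader might infer that 0.756 to 1.323 can only be a two-year OR. Without the simulated event rate this does not follow, because a one-year contrast at 2% risk gives the same limits. Indications of intent do not replace a named contrast in a confirmatory rule.

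**Conclusion.** The point holds as a defect in the primary decision rule: the OR tested against 1.4 is not identified. The aliasing and the multiplicity of ORs are exact and need no assumptions.

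The size is conditional. At true OR 1 and an assumed 1% risk, the upper limit is about 1.32 with about a 65% chance of meeting the margin for the averaged contrast or the model without the interaction. For the treatment-coded group coefficient it is about 1.49 or higher, with about a 24–36% chance. These figures rest on an equal split of centres between sequences (the SAP gives 36 centres but no allocation ratio), equal years, between-centre SDs of 0 to 0.5, and the stated limits being a two-year figure. The SAP's departmental range of 0.5% to 5.1% shows that centres differ, but it includes sampling noise and does not fix the SD. At a higher risk the one-year limit falls: in closed form without centre variance, 1.433 at 1.2% and 1.396 at 1.4%. The choice of contrast can therefore change the primary conclusion, so it should be fixed before the randomization code is opened.

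**What to change.** Either of two changes is enough:

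1. Define the primary OR as the group effect from a model with group, period and random centre. Keep group×period, if wanted, only in a supportive model labelled as a sequence or carry-over check.
2. If the term stays in the primary model, state that the OR tested against 1.4 is the equally weighted group contrast averaged over both periods.

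Use the same wording in Confidence intervals and p-values, Analysis methods and the Table 2 footnote. State the event rate and the contrast behind the limits 0.756–1.323 and 0.731–1.368. The cost is a few lines of SAP text and one line of model code, with no new data.
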